1. SYNOPSIS

Name of Sponsor: PellePharm, Inc.

Name of Investigational Product: patidegib gel

Name of Active Ingredients: patidegib HCl

Title of Study: Double-Blind, Dose Escalating, Randomized, Vehicle-Controlled Proof of Concept Clinical Trial of Patidegib Gel 2%, 4%, and Vehicle Applied Once or Twice Daily to Decrease GLI1 Biomarker in Sporadic Nodular Basal Cell Carcinomas

Number of Clinical Centers: One investigational center (metasite) in the United States will participate in this study.

Objective:

The primary objectives of the study are to evaluate the following:

- 1. The safety and tolerability of treatment with patidegib gel 2%, 4%, or vehicle applied once or twice daily for 12 weeks.
- 2. The molecular efficacy of treatment as defined by reduction in the hedgehog (HH) signaling pathway (GLI1 biomarker) after treatment with patidegib gel 2%, 4%, or vehicle applied once or twice daily for 12 weeks to treatment-targeted BCCs.

The secondary objective of the study is to evaluate the following:

1. The clinical efficacy of patidegib as defined by the percent decrease in greatest diameter of baseline treatment-targeted basal cell carcinomas after 12 weeks of treatment. Treatment-targeted Basal Cell Carcinomas (BCCs) will be biopsied prior to treatment to confirm the clinical diagnosis of nodular BCC. Eligible tumors will have the clinical features of nodular BCC and prior to biopsy will be no less than 5 mm or greater than 15 mm in greatest diameter on the face (excluding the nose and periorbital skin) and no less than 9 mm or greater than 20 mm in greatest diameter at sites other than the face.

Exploratory objective:

- 1. To evaluate the utility of an investigator static global tumor assessment (ISGTA) in assessing the proportion of baseline treatment targeted basal cell carcinomas that are evaluated as being clear or almost clear.
- 2. To evaluate the utility of blinded assessment of change in BCC size using photographs

PellePharm, Inc. Dose Escalating Study in Sporadic Basal Cell Carcinomas

Methodology:

This is a double-blind, dose escalating, randomized, vehicle-controlled study designed to compare the efficacy and safety of patidegib gel 2% and 4% applied once or twice daily in comparison with that of vehicle.

Approximately 36 subjects who meet the study entry criteria will be enrolled into one of four sequential cohorts. As soon as one cohort has been completely enrolled, the next cohort will be enrolled. Each subject will treat no more than two previously untreated biopsy confirmed treatment-targeted nodular BCCs. If the subject has additional non-treatment targeted BCCs they can be treated surgically or with topical agents prior to or during the trial. Within each cohort subjects will be randomized in a 2:1 ratio to receive active or vehicle gel. The sequential cohorts will be:

- Cohort 1: patidegib gel 2% or vehicle, once daily
- Cohort 2: patidegib gel 4% or vehicle, once daily
- Cohort 3: patidegib gel 2% or vehicle, twice daily
- Cohort 4: patidegib gel 4% or vehicle, twice daily

The study drug will be applied topically to the treatment-targeted BCCs and a rim or adjacent skin for 12 weeks.

Information on reported and observed adverse events (AEs) will be obtained at each visit. An abbreviated physical examination (PE) will be performed at Baseline and Week 12.

The treatment-targeted BCCs will be identified by the Investigator at the Baseline visit and will be circled in ink at Baseline, Weeks 6 and 12, and photographed, and measured at all study visits (Baseline, Weeks 2, 6, 8, 10, and 12).

Blood samples for complete blood count and serum chemistry and urine for urinalysis will be collected from subjects at Screening, Week 6, and Week 12.

Subjects who terminate study participation early will be asked to complete all Week 12 assessments, as appropriate, prior to commencement of any alternative therapy for BCCs (if possible). Subjects who discontinue from the study during the treatment period will not be replaced.

If signs or symptoms develop in the treatment areas during the treatment period that restrict daily activities or make continued application of the study drug difficult due to discomfort, the Investigator may instruct the subject to interrupt use of the study drug temporarily and to resume application of the study drug once the signs and symptoms have resolved adequately to the point that the Investigator believes that treatment can safely be resumed. The

Investigator should try to minimize study drug interruptions; and if needed, make best efforts to limit a "drug holiday" to 7 days. If the study drug interruption exceeds 4 consecutive days, the Investigator should consult with the Medical Monitor to determine a course of action. If the study drug is interrupted, discontinued, or a concomitant medication is used to treat a sign or symptom, an AE shall be recorded.

Subjects who discontinue from the study due to clinically significant laboratory abnormalities, AEs or any other reason will be asked to complete all Week 12 evaluations. Any subject who has an AE during the treatment period will be monitored by the Investigator until resolution (return to normal or to the baseline state) or stabilization, as determined by the Investigator.

In addition, application of study drug may be delayed or halted at any time if ongoing safety data evaluations raise concern for subject safety. If the subject participation is suspended, all of the subject's safety data will be reviewed by the Medical Monitor in conjunction with the Investigator to determine the course of action.

Number of Subjects Planned:

Approximately 36 subjects who meet the study entry criteria will be enrolled into one of four sequential cohorts.

Inclusion Criteria:

- 1. The subject is from 18 to 85 years of age, inclusive.
- 2. The subject must provide electronic informed consent prior to any study procedures.
- 3. If the subject is a woman of childbearing potential¹, she is willing to use two effective methods of birth control during the duration of the trial and for one month after the last application of the gel. The two forms of birth control authorized are defined as the use of a barrier method of contraception (condom with spermicide) in association with one of the following methods of birth control: bilateral tubal ligation; combined oral contraceptives (estrogens and progesterone) or implanted or injectable contraceptives with a stable dose for at least 1 month prior to Baseline; hormonal intra-uterine device (IUD) inserted at least 1 month prior to Baseline. This proscription is based on the key role of the HH pathway in embryogenesis, the known preclinical teratogenic effects of systemic cyclopamine, a naturally

¹ For the purpose of this trial, a female not of childbearing potential is defined as a sexually mature woman who: 1) has undergone a hysterectomy or bilateral oophorectomy; or 2) has been naturally postmenopausal for at least 12 consecutive months (i.e., has not had menses at any time in the preceding 12 consecutive months); or 3) is 41 years of age or older with physiologic symptoms of menopause and a Follicle Stimulating Hormone (FSH) level of ≥ 30 IU/L or 4) whose male sexual partner has had a vasectomy.

occurring inhibitor of SMO, and the unknown level of systemic exposure following topical application of patidegib in humans.

- 4. If the subject is a male with a female sexual partner who is of childbearing potential, the couple is willing to use two effective methods of birth control during the duration of the trial and for one month after the last application of the gel. Authorized birth control methods are outlined in Inclusion Criterion #3. Any woman of childbearing potential applying the gel to themselves, or assisting a subject, must comply with the same birth control measures.
- 5. One or two previously untreated BCCs with the clinical features of a nodular BCC confirmed by a biopsy done at or prior to screening confirming nodular BCC. These tumors must be suitable for surgical excision. The BCCs prior to biopsy must be no less than 5 mm or greater than 15 mm in greatest diameter on the face and no less than 9 mm or more than 20 mm in greatest diameter at sites other than the face. Tumors on the nose, periorbital skin, or on or below the knee are excluded.
- 6. The subject is willing to abstain from application of non-study topical prescription and over the counter medications within 5 cm of a treatment-targeted BCC for the duration of the study except as prescribed by the Investigator. Moisturizers and emollients are allowable. Subjects will be encouraged to use sunscreen with a sunscreen protection factor (SPF 15 or higher) at least once daily on all exposed skin sites.
- 7. Female subjects must have negative serum pregnancy test at Screening.
- 8. The subject is willing to contact the study center after each primary skin care physician (PSCP) visit to provide the study center details of the visit and any treatment of skin tumors.
- 9. The subject is willing to forego alternative treatment of the treatment-targeted baseline BCC for the duration of the trial.

Exclusion Criteria:

- 1. Subjects with basal cell nevus syndrome (BCNS, Gorlin syndrome, nevoid basal cell carcinoma syndrome; OMIM #109400).
- 2. The subject has used topical products within 5 cm of a treatment- targeted BCC or systemic therapies that might interfere with the evaluation of the study medication during the study. Specifically, these include the use of:
 - a. Topical glucocorticoids 30 days prior to screening
 - b. Retinoids (e.g., etretinate, isotretinoin, tazarotene, tretinoin, adapalene) systemically or topically, or > 5% of an alphahydroxy acid (e.g., glycolic acid, lactic acid), photodynamic therapy (PDT), or 5-fluorouracil or imiquimod (except as topical treatment to discrete BCCs) systemically or topically to the skin during the six months prior to entry.
 - c. Systemic chemotherapy within one year prior to screening. (Note: field therapy with topically applied treatments can be done as long as they are not applied within 5 cm of a treatment-targeted tumor).
 - d. Known inhibitors of the HH signaling pathway (e.g., vismodegib, patidegib, sonidegib, and itraconazole) topically or systemically within 6 months of entry into the study.
- 3. The subject has a history of hypersensitivity to any of the ingredients in the study medication formulation.
- 4. The subject is unable or unwilling to make a good faith effort to be present for all follow-up visits and tests.
- 5. The subject is a woman who is currently nursing.
- 6. The subject has any systemic disease that in the Investigator's opinion would interfere with the subject's ability to participate.
- 7. The subject has a clinically significant history of liver disease, including viral hepatitis, current alcohol abuse, or cirrhosis that in the investigator's opinion would interfere with the subject's ability to participate.
- 8. The subject has any condition or situation, which in the Investigator's opinion may put the subject at significant risk, could confound the study results, or could interfere significantly with the subject's participation in the study. This includes history of other

skin conditions or diseases, metabolic dysfunction, physical examination findings, or clinical laboratory findings giving reasonable suspicion of a disease or condition that contraindicates use of this investigational drug or that might affect interpretation of the results of the study or render the subject at high risk from treatment complications.

- 9. The subject has a history of invasive cancer within the past five years excluding non-melanoma skin cancer, Stage I cervical cancer, ductal carcinoma in situ of breast, or chronic lymphocytic lymphoma (CLL) (Stage 0).
- 10. The subject is currently participating in an experimental drug study, (within 4 weeks of Baseline visit), or plans to participate in an experimental drug study while enrolled in this study.
- 11. The subject is on a concomitant medication that is a strong CYP3A4 inhibitor. These include, but are not limited to: larithromycin, telithromycin, nefazodone, itraconazole, ketoconazole, atazanavir, darunavir, indinavir, lopinavir, nelfinavir, ritonavir, saquinavir, and tipranavir.

Investigational Product, Reference Therapy, Dosage and Mode of Administration:

- patidegib gel 2%, applied topically, once daily for 12 weeks
- patidegib gel 4%, applied topically, once daily for 12 weeks
- patidegib gel 2%, applied topically, twice daily for 12 weeks
- patidegib gel 4%, applied topically, twice daily for 12 weeks
- vehicle gel, applied topically, once daily for 12 weeks
- vehicle gel, applied topically, twice daily for 12 weeks

Application Instructions:

The Investigator or their designee will instruct the subject on how to apply the study drug to the previously biopsied treatment-targeted BCCs identified at the Baseline visit by the Investigator. The staff member will instruct the subject on the proper application procedure during the Baseline visit. The quantity of gel to be applied will be defined using laminated dosing cards. Approximately 20 mg of gel will be applied to each tumor at each treatment. The subject is to treat no more than two treatment-targeted BCCs. If the subject has additional BCCs they may be treated surgically or topically during the trial. In addition to the verbal instructions given during the visit, the subjects will be provided with written instructions for proper application technique.

Because sunlight can increase the development of skin cancers subjects will be advised to avoid or minimize exposure to direct sunlight while in the study. Subjects will also be advised to wash their hands before and after application of the study drug.

The amount of study drug used by the subjects will be guided by instructing the subjects to use dosing cards that will provided to them, and monitored by weighing each newly dispensed study drug tube, and re-weighing each returned study drug tube.

Duration of Treatment:

All subjects will be treated for 12 weeks.

Criteria for Evaluation:

The study will be conducted as outlined in the Schedule of Assessments (Table 1). For all efficacy measurements, the Investigators will be provided with study specific training to ensure consistent evaluations. The assessments for a particular subject should be performed by the same investigator at all study visits whenever possible.

Safety Measurements:

Dermal Safety and Tolerability: Safety and tolerability will be evaluated through assessment of selected local signs and symptoms (pain / burning, pruritus, erythema, edema, and scabbing / crusting). Each of the identified BCCs will be evaluated separately for these signs and symptoms of application site reactions. Any local skin reaction that requires use of a concomitant therapy or causes study drug interruption or discontinuation should be reported as an AE. The scales to be used for assessing local skin reactions at treatment sites follow:

Score	Grade	Description
experie	Ü	eported by the subject as being the greatest intensity they have application site within the last 24 hours at Baseline or since the last visits.
0	None	No pain/burning
1	Mild	Slight burning/stinging sensation; not really bothersome
2	Moderate	Definite warm, burning/stinging that is somewhat bothersome
3	Severe	Hot burning/stinging sensation that causes definite discomfort and may interrupt daily activities and/or sleep
experie	-	ed by the subject as being the greatest intensity they have application site within the last 24 hours at Baseline or since the last visits.
0	None	No pruritus
1	Mild	Slight pruritus, not really bothersome
2	Moderate	Definite pruritus that is somewhat bothersome
3	Severe	Intense pruritus that may interrupt daily activities and/or sleep
Eryther	na: as asses	sed by the Investigator at each site
0	None	No erythema present
1	Mild	Slight pink coloration
2	Moderate	Definite redness
3	Severe	Marked erythema, bright red to dusky dark red in color
Score	Grade	Description
Edema.	as assessed	d by the Investigator at each site
0	None	No edema

1	Mild	Slight, but definite edema	
2	Moderate	Definite edema	
3	Severe	Marked edema	
Scabbing/Crusting: as assessed by the Investigator at each site			
0	None	No scabbing/crusting	
1	Mild	Slight, but definite scabbing/crusting	
2	Moderate	Definite scabbing/crusting	
3	Severe	Marked scabbing/crusting	

Symptoms of Hedgehog Inhibitor Toxicity: At each visit subjects will be asked if they have experienced any symptoms that have been associated with systemic use of this class of drugs, in particular hair loss, taste loss, muscle cramps, bowel changes, fatigue.

Adverse Events: During the study, subjects will be assessed for the occurrence of new and ongoing AEs. Descriptions of AEs will include the dates of onset and resolution (if resolved), maximum severity, and seriousness, action taken regarding the study drug, corrective treatment, outcome, and the Investigator's assessment of causality. AEs present at any visit will be followed to resolution (return to normal or to the baseline state) or until clinically stable as determined by the Investigator.

Safety Laboratory Tests: Routine safety laboratory tests (complete blood count/differential urinalysis and serum chemistry) will be performed at Screening, Week 6, and Week 12. Any out-of-range laboratory result that is considered clinically significant by the Investigator will be recorded as an AE and should be confirmed by repeat testing at the discretion of the Investigator. Clinically significant laboratory abnormalities at any visit will be followed to resolution (return to normal or to the baseline state) or until clinically stable as determined by the Investigator.

Physical Examinations: An abbreviated physical examination including measurements of height, weight, and vital signs (blood pressure, heart rate, respiration rate, and oral temperature) will be performed at Baseline and Week 12.

Pregnancy Tests: All female subjects will have a pregnancy test performed at the Screening visit. Females of childbearing potential will take a home pregnancy urine test at Weeks 2, 8, and 10 and will have a serum pregnancy test at Weeks 6 and 12.

Efficacy Measurements:

Primary:

Biomarker: At screening the treatment-targeted BCC will be biopsied to confirm the clinical diagnosis of nodular BCC. In addition, at or within 14 days of the Week 12 visit the

treatment site will be excised. Both of these tissue samples will be tested for GLI1 mRNA levels.

Secondary:

The clinical efficacy of patidegib as defined by the percent decrease from Baseline of the longest diameter of treatment-targeted BCC after 12 weeks of treatment.

Exploratory:

- To evaluate the utility of an investigator static global tumor assessment (ISGTA) in assessing the proportion of baseline treatment-targeted BCCs that are evaluated as being clear or almost clear.
- Histologic Cure: The proportion of the excisional samples obtained at or shortly after the Week 12 visit that demonstrate no residual BCC.

Statistical Methods:

All subjects who are randomized and dispensed study drug will be included in the intent-to-treat (ITT) analysis set. All subjects who are randomized, receive at least one confirmed dose of study drug, and have at least one post-baseline safety assessment will be included in the safety population.

No imputation will be made for the primary endpoint. For the secondary endpoint, last observation carried forward (LOCF) will be used to impute efficacy data that are missing post-baseline through Week 12. No imputations will be made for missing safety data.

Per protocol analysis will be performed – we will exclude samples with insufficient BCC, subjects with poor treatment compliance, or tumors where the diameter was incorrectly measured based on review of photographs. We will also analyze BCC size change based on photographs.

Efficacy Summaries:

The efficacy endpoints are intended to compare once and twice daily application of 2% patidegib gel, 4% patidegib gel, and vehicle gel. Efficacy assessments will be summarized descriptively by treatment group and visit.

Primary Efficacy Endpoints:

• Change in GLI1 mRNA levels in drug-treated vs. vehicle-treated tumors after 12 weeks of treatment.

Secondary Efficacy Endpoint:

• Decrease in tumor size defined as percent decrease in the greatest diameter of baseline treatment-targeted BCCs at the Week 12.

Exploratory Efficacy Endpoint:

- The proportion of baseline treated tumors are smaller based on photographic review
- The proportion of baseline treatment targeted BCCs that are evaluated as being clear or almost clear at Baseline, Weeks 2, 6, 8, 10, and 12 based on the ISGTA.

Efficacy Analyses:

The primary endpoint and the secondary endpoints of change in tumor size, and reduction in the HH signaling pathway will be evaluated with an analysis of covariance (ANCOVA) with treatment group as factor and baseline value as a covariate. Pairwise comparisons will be performed using contrasts within the ANCOVA. Additionally, t-tests for pairwise comparisons of the primary endpoint will be done, or alternatively a non-parametric approach may be used.

The exploratory analysis of ISGTA will be analyzed with a Cochran-Mantel-Haenszel test

Safety:

Safety Endpoints:

- Adverse Events
- Dermal Safety and Tolerability including pain/burning, pruritus, erythema, edema, and scabbing/crusting
- Clinical laboratory assessments

Safety Analyses:

Subjects will be assessed for the occurrence of new and ongoing AEs. Descriptions of AEs will include the dates of onset and resolution (if resolved), maximum severity, seriousness, action taken regarding the study drug, corrective treatment, outcome, and Investigator's assessment of causality. All AEs will be recorded and classified using terminology from the Medical Dictionary for Regulatory Activities (MedDRA). All reported treatment-emergent AEs (TEAEs), defined as any AE with an onset on or after the date of first study drug application, will be summarized by treatment group, the number of subjects reporting TEAEs, system organ class, preferred term, severity, and relationship to study drug. When summarizing TEAEs by severity or relationship to study drug, each subject will be counted only once within a system organ class or a preferred term using the event with the greatest severity or causality, respectively, within each category. All reported serious adverse events

(SAEs) will be summarized by treatment group, the number of subjects reporting SAEs, system organ class, preferred term, severity, and relationship to study drug.

All information pertaining to AEs noted during the study will be listed by subject and will include a verbatim description of the event as reported by the Investigator, as well as the preferred term, system organ class, start date, stop date (if stopped), seriousness, severity, action taken regarding the study drug, corrective treatment, outcome and relationship to the study drug. In addition, a listing of subjects who prematurely discontinue from the study due to AEs will be provided as well as a listing of subjects who reported an SAE.

The frequency of dermal safety and tolerability assessments including pain/burning, pruritus, erythema, edema, and scabbing/crusting will be summarized by treatment group and visit.

Changes from baseline in safety laboratory values and vital sign measurements will be summarized with descriptive statistics for each treatment group at all applicable study visits.

Shift tables will be presented for changes in safety laboratory values to summarize laboratory test results collected at Screening and Weeks 6 and 12. Normal ranges established by the central laboratory will be used to determine the shifts. A listing of all out-of-range laboratory test results at any assessment time point will also be provided. Determination of clinical significance for all out-of-range laboratory values will be made by each Investigator and included in the listing. In addition, a listing of all clinically significant laboratory test results will be provided.

Sample Size Calculations:

This is a dose ranging study.

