4. INTRODUCTION

PellePharm, Inc. is developing patidegib gel for the management of the burden of disease in patients with basal cell nevus syndrome (BCNS), a rare genetic disease characterized by the development of numerous basal cell carcinomas over a lifetime. This trial will evaluate the ability of patidegib gel to shrink BCC tumors in patients with sporadic BCCs as a proof-of-concept for the mechanism of patidegib on BCCs. It is hoped that results from this study will inform the dose and dosing regimen prior for future trials, thereby maximizing the therapeutic potential.

Basal cell carcinomas: These tumors are the most common of human cancers, occurring in an estimated 2-3 million Americans each year. The overwhelming majority of these tumors occur sporadically with a strong predilection for sun exposed skin sites in persons of Northern Europe descent who have had excessive sun exposure. Sporadic BCCs are most commonly seen starting in the 4th decade of life. Current treatment depends in large part on physical destruction of the tumors, most commonly with surgery and less commonly with ionizing radiation.

Basal cell nevus syndrome: BCCs are one of the most prominent phenotypic features of patients with the BCNS (Gorlin) syndrome (OMIM #109400]¹. This syndrome is inherited as an autosomal dominant condition, and patients are susceptible to many abnormalities, including, most frequently, palmar and plantar pits and jaw cysts, and medulloblastomas. Reports of its prevalence vary; the highest estimate is 1:31,000. In one study of patients with heritable cancer syndromes studies, those with BCNS had the longest expected lifespan of 73 years², which is not unexpected for a cancer that grows locally and metastasizes only very rarely. Diagnosis of BCNS commonly is made when patients are in their teens³. The burden of BCCs varies among BCNS patients. For example, in a Children's Hospital Oakland and Stanford combined registry of 100 BCNS patients living throughout the United States, 1/3 had a total of 5 or fewer BCCs in the previous two years, 1/3 had 6-20 BCCs treated, and 1/3 had more than 20 BCC in the past 2 years³.

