Subjects will return their tubes of study drug, which will be evaluated for drug usage compliance. While individual usage rates of topical products will vary, the use of a dosing card should help limit the variation in dosing inherent with topical products. Approximately 20 mg of the gel represents a single applied dose. Thus a subject treating a single tumor once daily for 12 weeks will apply a total dose of 1.6 gm of gel and those treating two tumors twice daily for 12 weeks will apply a total dose of 6.4 gm of gel. In terms of actual drug, 20 mg of patidegib gel 2% and 4% contains 0.4 mg and 0.8 mg of patidegib, respectively. Thus the total dose of drug in the 2% once daily group treating a single tumor will be approximately 34 mg while subjects treating two tumors twice daily for 12 weeks with patidegib gel 4% will receive a total of 134 mg of patidegib. To put this in perspective in previous trials with an oral formulation of patidegib subjects were treated with a daily oral dose of 130 – 160 mg, many for longer than 6 months.

Upon completion of the 12-week treatment period, all subjects will be asked to return to the investigational center for final evaluation. At the Week 12 visit the treatment site(s) will be excised. The area excised should at a minimum include the original diameter of the tumor. This means that if the tumor has shrunk in size the entire original area of the BCC will be excised, not just the visually apparent residual tumor. During the study, subjects will be allowed to use moisturizers and emollients and sunscreen. The Investigator will assess the areas affected at each visit.

The treatment-targeted BCC(s) will be identified by the Investigator at the Baseline visit and will be circled in ink at Baseline, Weeks 6 and 12, and photographed, and measured at all study visits (Baseline, Weeks 2, 6, 8, 10, and 12).

Biomarkers: On each subject one or two baseline previously untreated nodular BCCs designated as a treatment-targeted tumor will be biopsied and at the end of 12 weeks of treatment the treatment

PellePharm, Inc.

Dose Escalating Study in Sporadic Basal Cell Carcinomas

site(s) will be excised. Both samples will be evaluated histologically and for determination of GLI1 mRNA levels.

Blood samples for complete blood count and serum chemistry and urine for urinalysis will be collected from subjects at Screening, Week 6, and Week 12.

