Measure and Map BCCs	X	X	X	X	X	X	X	
Determine Clinical Tumor Type	X							
2mm Punch or Shave Biopsy	X							
End of Treatment Excision							Xh	
BCC Imaging ^I	X	X	X	X	X	X	X	

PellePharm, Inc.

Dose Escalating in Sporadic Basal Cell Carcinomas

Systemic Symptoms		X	X	X	X	X	X	
Patidegib /Vehicle Applications ^J		X	X	X	X	X		
Study drug review/Instructions Dispensation ^J		X	Х	х	х	Х		
Concomitant Medications	X	X	X	X	X	X	X	
Adverse Events	X	X	X	X	X	Х	X	
Review Test Article Compliance/Accountability		X	х	Х	Х	Х	Х	
Clinical Evaluation of Surgical Site(s)								X

BCC= basal cell carcinoma; ET = early termination; ISGTA = investigator static global tumor assessment;

- a for subjects who discontinue early during the treatment period, all procedures outlined for the ET visit should be completed at the time of discontinuation.
- b Must be signed prior to any study procedures.
- ^c Medical history will be updated at Baseline visit.
- d Height will be measured at Baseline only.
- ^e Blood samples for laboratory tests will be collected at Screening. Clinically significant laboratory findings at Week 6 or Week 12 will be repeated at the discretion of the Investigator, and the subject will be followed until resolution (return to normal or to the baseline state) or until clinically stable as determined by the Investigator.
- f Week 6 and 12 serums to be done only for women of child bearing potential
- 8 Only to be done for women of child bearing potential
- h Must be within 48 hours of the Week 12 visit.
- ¹ Imaging requirements are provided in the imaging manual.
- Jubjects will be trained on how to administer the study drug at the Baseline visit and retrained at subsequent visits, if necessary. The study drug may be applied at the study visit. Subjects will record any missed doses and provide to the study site for review

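### A woman counted as not of childbearing potential because of her partner's vasectomy has no scheduled pregnancy test after Screening, although she may be fertile

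*Protocol*

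**What the plan says.** Inclusion Criterion 3 requires of a woman of childbearing potential that "she is willing to use two effective methods of birth control during the duration of the trial". One is a barrier method, used "in association with one of the following methods of birth control: bilateral tubal ligation" or one of the listed hormonal methods. The reasons given are the role of the hedgehog pathway in embryogenesis, the preclinical teratogenicity of systemic cyclopamine, and unknown systemic exposure after topical use.

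The footnote to that criterion, identical in the Synopsis and Section 6.1, gives four ways of being not of childbearing potential: hysterectomy or bilateral oophorectomy; natural menopause for at least 12 months; age 41 or older with menopausal symptoms and an FSH of at least 30 IU/L; or being a woman "whose male sexual partner has had a vasectomy".

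Criterion 7 covers every woman before dosing: "Female subjects must have negative serum pregnancy test at Screening". Later tests are narrower. A note to Table 1 reads "Week 6 and 12 serums to be done only for women of child bearing potential", and the note on the home urine test sets the same limit. Section 9.3.4 and the Synopsis repeat the restriction. Section 9.1.2, item 13, gives the three home kits only to women of childbearing potential.

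Sections 6.3 and 6.4 require study drug to stop if a subject becomes pregnant.

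**The concern.** Items 1 to 3 describe the woman's own reproductive status. Item 4 describes another person's. A partner's vasectomy is a form of contraception and leaves her own fertility unchanged, but the footnote uses it to reclassify her. That one classification switches off two separate safeguards: the two-method rule, for which an exemption can be argued, and the pregnancy testing, which exists to catch contraceptive failure.

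The comparison with tubal ligation shows the inconsistency. A woman who has herself been sterilised by ligation still counts as of childbearing potential, still needs a barrier method and has every later test. A woman whose partner has been sterilised needs neither.

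What is at stake is detection. Stopping drug at pregnancy protects the fetus only once the pregnancy is known, and for this woman no scheduled procedure during dosing is designed to find it.

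**Working it through.** **Length of dosing.** The protocol treats for 12 weeks: 12 × 7 = 84 days. Table 1 puts Week 12 at Day 85 ± 3, and 85 − 1 = 84 agrees. With the visit window the range is 82 − 1 = 81 to 88 − 1 = 87 days. As a cross-check, Section 5.1 gives about 34 mg for one tumor treated once daily with 2% gel: 0.4 mg × 84 = 33.6 mg.

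**Scheduled pregnancy tests after Screening** (Table 1, Section 9.3.4):

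| Test | Nominal day | Of childbearing potential, including tubal ligation | Classed under item 4 |
|---|---|---|---|
| Week 2 urine | 15 | yes | no |
| Week 6 serum | 43 | yes | no |
| Week 8 urine | 57 | yes | no |
| Week 10 urine | 71 | yes | no |
| Week 12 serum | 85 | yes | no |
| Total | | 5 of 5 | 0 of 5 |

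**Longest time without a test.**
- Woman of childbearing potential, from Day 1: gaps of 14, 28, 14, 14 and 14 days, which sum to 84. The longest is 28 days (Week 2 to Week 6). With windows it is at most Day 46 − Day 13 = 33 days.
- Woman under item 4: the whole 84 days. Her only test is at Screening, on Day −42 to Day 0, and no pregnancy test is scheduled at Baseline. At the nominal end of dosing that test is 0 + 84 = 84 to 42 + 84 = 126 days old, or up to 42 + 87 = 129 days with a late Week 12 visit.

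**Applied dose.** Section 5.1 states that "20 mg of patidegib gel 2% and 4% contains 0.4 mg and 0.8 mg of patidegib", respectively. The highest regimen is 4% gel on two tumors twice daily: 0.8 × 2 × 2 = 3.2 mg/day. Against the earlier oral dose of 130 to 160 mg/day this is 3.2/160 = 2.0% to 3.2/130 = 2.5%. Over 84 days it totals 3.2 × 84 = 268.8 mg. Section 5.1 gives 134 mg for this regimen, which is about 134/84 = 1.6 mg/day. The two figures conflict, but the dose is low on either, and the larger is used here. The absorbed fraction is not given.

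**Number affected.** Not stated. About 36 subjects are planned, 6 active and 3 vehicle in each of four cohorts, so about 24 on active drug. The Introduction says "Sporadic BCCs are most commonly seen starting in the 4th decade of life", while eligibility begins at age 18. The count is probably small and may be zero.

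**Effect on the analysis.** None. Protocol Section 10.8.4 puts pregnancy results in a listing only.

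**The case against.** The strongest reply is that item 4 is deliberate. The footnote defines the term for this trial, appears identically in two places, and explains why vasectomy is absent from the contraceptive list in criterion 3. Vasectomy is contraception, so exempting the couple from two further methods is defensible. This stands for the contraception rule and is why the fix keeps the exemption. It gives no reason to drop the tests.

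A reader might infer that the protocol accepts an unverified vasectomy, or knowingly admits women with several partners. The documents do not support either reading. The footnote is silent on proof, but it is equally silent on proof of hysterectomy or oophorectomy, and criterion 3 asks for no proof of tubal ligation. Eligibility is verified at Screening and again at Baseline. The footnote speaks of a single partner, and criterion 4 of a couple. Stating confirmation and sole partnership would be a useful clarification; their absence does not show that unconfirmed claims would be accepted.

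Other safeguards exist: the negative Screening test, the Investigator's discretion under Exclusion 8, questions on nausea, vomiting and fatigue at post-baseline visits, and the mandatory stop at pregnancy. They lower the risk. None is a scheduled pregnancy test, and the stop rule depends on detection.

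A reader might also infer a material risk of fetal harm. The documents give no vasectomy failure rate, no absorbed fraction and no count of women affected, so that probability cannot be estimated from them. The gap can be measured only in tests and days.

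**Conclusion.** The point holds as a gap in pregnancy monitoring. Following the rules as written, a possibly fertile woman classed under item 4 has 0 of 5 scheduled tests over a nominal 84 days (81 to 87 with the window), against 5 of 5 for a woman with tubal ligation, whose longest nominal gap is 28 days. This follows from the stated rules and does not depend on whether the vasectomy was confirmed.

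It rests on two assumptions: that sites apply the footnote literally, and that at least one enrolled woman qualifies under item 4 while meeting none of items 1 to 3. If no such woman enrols, nothing happens. The likelihood of harm is low and unquantified. The change is still worth making because the sponsor judged five tests appropriate for other fertile women on the same dose and because the remedy costs little. It is a subject-safety point with no bearing on endpoints, sample size or analysis.

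**What to change.** In both footnotes, keep item 4 only as an exemption from the two-method contraception rule, and word it as a sole male partner with a confirmed-successful vasectomy. In Table 1 (both pregnancy-test notes), Section 9.1.2 item 13, Section 9.3.4 and the matching Synopsis text, state that female subjects exempted under item 4 still have the five scheduled pregnancy tests and receive the three home kits.

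Deleting item 4 outright is the less suitable change. The same definition governs criterion 4 ("If the subject is a male with a female sexual partner who is of childbearing potential") and women who help apply the gel. Deletion would put the two-method rule on couples in which the male subject himself has had a vasectomy, and on helpers. It would also leave open whether vasectomy replaces one method or both. Limiting the new sentence to female subjects and to testing avoids this.

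The cost is the wording above and, for each woman affected, up to three home urine tests, two serum tests at Weeks 6 and 12 when blood is already drawn, and confirmation of the vasectomy.
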